APPENDIX D:

23.4 Rating scales

23.4.1 Expanded Disability Status Scale (EDSS)

0.0	Normal neurological examination
1.0	No disability, minimal signs in one FS
1.5	No disability, minimal signs in more than one FS
2.0	Minimal disability in one FS
2.5	Mild disability in one FS or minimal disability in two FS
3.0	Moderate disability in one FS, or mild disability in three or four FS. Fully ambulatory
3.5	Fully ambulatory but with moderate disability in one FS and more than minimal disability in several others
4.0	Fully ambulatory without aid, self-sufficient, up and about some 12 hours a day despite relatively severe disability; able to walk without aid or rest some 500 meters
4.5	Fully ambulatory without aid, up and about much of the day, able to work a full day, may otherwise have some limitation of full activity or require minimal assistance; characterized by relatively severe disability; able to walk without aid or rest some 300 meters.
5.0	Ambulatory without aid or rest for about 200 meters; disability severe enough to impair full daily activities (work a full day without special provisions)
5.5	Ambulatory without aid or rest for about 100 meters; disability severe enough to preclude full daily activities
6.0	Intermittent or unilateral constant assistance (cane, crutch, brace) required to walk about 100 meters with or without resting
6.5	Constant bilateral assistance (canes, crutches, braces) required to walk about 20 meters without resting
7.0	Unable to walk beyond approximately five meters even with aid, essentially restricted to wheelchair; wheels self in standard wheelchair and transfers alone; up and about in wheelchair some 12 hours a day
7.5	Unable to take more than a few steps; restricted to wheelchair; may need aid in transfer; wheels self but cannot carry on in standard wheelchair a full day; May require motorized wheelchair
8.0	Essentially restricted to bed or chair or perambulated in wheelchair, but may be out of bed itself much of the day; retains many self-care functions; generally has effective use of arms
8.5	Essentially restricted to bed much of day; has some effective use of arms retains some self care functions
9.0	Confined to bed; can still communicate and eat.
9.5	Totally helpless bed patient; unable to communicate effectively or eat/swallow
10.0	Death due to MS

23.4.2 Scripps NRS

Scripps NRS		Maximum points	Normal	Degree of impairment		
				Mild	Mod.	Severe
Systems Examined						
Mentation and Mood:		10	10	7	4	0
Cranial nerves:	Visual acuity	21	5	3	1	0
	Fields, Discs, Pupils		6	4	2	0
	Eye movements		5	3	1	0
	Nystagmus		5	3	1	0
Lower cranial nerves:		5	5	3	1	0
Motor:	RU	20	5	3	1	0
	LU		5	3	1	0
	RL		5	3	1	0
	LL		5	3	1	0
Deep Tendon Reflexes:	UE	8	4	3	1	0
	LE		4	3	1	0
Babinski: R&L (2 for each)		4	4	-	-	0
Sensory:	RU	12	3	2	1	0
	LU		3	2	1	0
	RL		3	2	1	0
	LL		3	2	1	0
Cerebellar:	UE	10	5	3	1	0
	LE		5	3	1	0
Gait: Trunk and balance:		10	10	7	4	0
Bladder/Bowel/Sexual dysfunction:		0	0	-3	-7	-10
Scripps NRS total score:						

23.5 Modified McDonald's Diagnostic Criteria for PP-MS

(Polman, Reingold et al. 2005)

- 1) One year of disease progression (retrospectively or prospectively determined)
- 2) *Plus* two of the following:
 - a. Positive brain MRI (≥ 9 T2 lesions or ≥ 4 T2 lesions with positive VEP)
 - b. Positive spinal cord MRI (≥ 2 focal T2 lesions)
 - c. Positive CSF (isoelectric focusing evidence of oligoclonal IgG bands or increased IgG index, or both)

As with RR-MS, the alternative diagnoses that could explain insidious progression of neurological disability or MRI/CSF findings need to be searched for and ruled out before the diagnosis of MS can be concluded.

Do you have Primary Progressive Multiple Sclerosis?

If so, you may qualify for an NIH research study.

The Neuroimmunology Branch (NIB) of the National Institutes of Health is conducting a study to investigate the efficacy of an oral experimental drug in primary progressive multiple sclerosis. The study will be conducted at the NIH Clinical Center in Bethesda, Maryland, on an outpatient basis.

We are seeking participants:

- ages between 18-65
- diagnosis of Primary Progressive Multiple Sclerosis
- not taking any immunomodulatory drugs

The study involves a one year baseline after which participants will receive the medication or placebo for 2 years. Medical evaluations, MRIs, and blood work will be performed at scheduled intervals during the 3-year study. The visits will last 2-5 hours each and will be every month the first 3 months and then every 6 months for the remainder of the study.

There is no cost for participation.

Travel reimbursement will be provided.

Please call [contact] for more information about participating in this study. Please refer to study number 09-N-0197. [www. ClinicalTrials.gov](http://www.ClinicalTrials.gov)

Do you have Primary Progressive Multiple Sclerosis?

Researchers at the NIB are seeking adults ages 18-65 with a diagnosis of Primary Progressive Multiple Sclerosis to participate in a randomized, placebo controlled, double blind study investigating the efficacy of Idebenone in this disease. Participation will include medical evaluations, MRI, bloodwork, and lumbar puncture performed at the NIH Clinical Center on an outpatient basis.

Q. What's involved in the study?

We are seeking patients age 18-65 who have a diagnosis of primary progressive multiple sclerosis and who are not on immunomodulatory treatment. The study will last three years. Upon entering the study, patients will undergo serial MRI studies and clinical examinations which will be performed monthly for 3 months. Following this, patients will enter a pre-treatment phase of 12 months duration, during which clinical visits, MRI imaging and blood work will be performed every 6 months. Patients will then be randomized to receive treatment or placebo, with continued monitoring by clinical exam, MRI and bloodwork at scheduled intervals. In addition to the MRI imaging and clinical exams, participating patients will undergo a spinal tap at the time of enrollment and again after one year of treatment.

Idebenone (2,3-dimethoxy-5-methyl-6-(10-hydroxydecyl)-1,4-benzoquinone) is a synthetic analogue of coenzyme Q10, which is an indispensable constituent of the mitochondrial electron-transport chain and also cell membrane antioxidant. Idebenone has been extensively studied as a potential therapeutic agent for neurological diseases, including Alzheimer's disease, Huntington's disease, Friedrich's ataxia and multi-infarct dementia. In these clinical trials, in which a variety of doses and dosing regimens were employed, idebenone was found to be safe and well tolerated. In these studies, the most frequently cited adverse effects that occurred more often in the idebenone group were gastrointestinal symptoms such as anorexia, nausea, and diarrhea.

If you know of any patients who might qualify for this study, we would greatly appreciate if you could provide the patient and their family member/caregiver with a copy of the enclosed advertisement so that they can contact us. We also plan to meet with as many professionals as possible to describe this study in further detail. Please contact us at [contact] if you would like further information regarding this study.

Sincerely,

Dear

23.7 MS Patient Questionnaire

Attached in PTMS.

23.8 Investigator's Brochure

Attached as pdf file or hard copy

23.9 Clinical trial agreement (CTA)

Attached as pdf file or hard copy

This Statistical Analysis Plan (SAP) describes the statistical analysis as it is foreseen prior to breaking the blind of this study. The SAP will serve as a compliment to the study protocol and supersedes it in case of differences. Any deviations from the statistical analyses planned in the most recent version of the study protocol (version 27, 13 April 2017) are documented in this SAP and any major deviations from the statistical analyses planned in the SAP will be documented in the final clinical study report.

3 Study objectives and hypotheses

The goal of this study is to assess the safety, therapeutic efficacy, and mechanism of action of idebenone in primary-progressive multiple sclerosis (PP-MS) patients. We hypothesize that idebenone, through its combined effect on facilitation of mitochondrial metabolism and limitation of oxygen radical-induced central nervous system (CNS) damage, will inhibit CNS tissue destruction in PP-MS patients.

3.1 Original goals of the study

The following goals were defined in the original study protocol.

The primary goals of the study were defined as:

1. To determine the safety of long-term (24 months) idebenone therapy at 2250 mg/day in patients with PP-MS.
2. To determine the efficacy of idebenone versus placebo in inhibiting individualized rates of CNS tissue destruction as measured by clinical biomarkers and quantitative imaging biomarker of brain atrophy (i.e. ventricular volume).

The secondary goals of the study were defined as:

1. To investigate the mechanism of action of idebenone in PP-MS.
2. To determine/define biomarkers of mitochondrial dysfunction and oxidative damage in PP-MS patients.
3. To define biomarkers indicative of therapeutic effect of idebenone on mitochondrial dysfunction and on limiting oxidative damage in PP-MS patients.
4. To collect longitudinal data in the placebo arm that will allow us to evaluate whether the assumptions on which we based our primary analysis (i.e. that the CNS tissue destruction is intra-individually linear, but inter-individually different within 3 year time period) are correct or not. This will allow us to calculate more precise sample size/power calculations for future neuroprotective trials in PP-MS.

3.2 Adaption of objectives and endpoints

The study was planned to use an adaptive trial design. The trial started with a pre-treatment baseline period of at least 12 months, where magnetic resonance imaging (MRI), clinical and biomarker measurements were collected in all patients for two purposes:

- To obtain longitudinal quantitative MRI, clinical and electrophysiological data in untreated PP-MS patients before randomization. These data will be utilized for the selection of the most sensitive primary outcome measure. This will be done on the first 30 patients and subsequent analysis will be used for selection of the most sensitive primary outcome measure and for adjusting sample size calculation if the primary outcome measure is different than brain atrophy measured by SIENA methodology.
- To obtain patient-specific pre-randomization baseline for all collected outcome measures. This is expected to increase the statistical power of the study ((Murray et al. 2005, Young et al. 2005, Frost et al. 2008). In the study protocol, the following two assumptions were made: 1) CNS tissue destruction develops in a linear manner within a 3-5 year time-frame in the majority of PP-MS patients and 2) the slopes of the linear development of CNS tissue destruction differ among individual patients. Based on these two assumptions, the trial design will allow adjustment for the individualized rates of development of CNS tissue destruction.

The aim of the adaptive trial design was to allow the selection of the most robust (i.e. most sensitive and most accurate) primary outcome measure for the final analysis. Based on the analysis of the pre-treatment phase, the focus of the study shifted from the analysis based on MRI to analysis of clinical endpoints and composite scores. For more details, see section 6 of this SAP.

3.3 Statistical hypothesis

The primary goal of this study is to determine the safety of long-term (24 months) idebenone therapy at 2250 mg/day in patients with PP-MS.

The primary efficacy objective of this final analysis of the IPPoMS study is to investigate the effect of idebenone compared with placebo on the disability progression using the CombiWISE score with the following statistical hypotheses:

H_0 : There is no difference between idebenone and placebo in the disability progression during the 2-year treatment period.

H_A : The disability progression in idebenone-treated patients is slower than in the placebo-treated patients during the 2-year treatment period.

In addition to the difference between the treatment groups, the within-group changes in each treatment group will be evaluated by comparing the disability progression during the pre-treatment period to the progression during the treatment period.

4 Endpoints

4.1 Primary safety endpoints

The primary safety endpoints include premature discontinuations of study treatment, serious adverse events and all adverse events. For more details on the analysis of the safety data, see Section 12 of this SAP.

4.2 Primary efficacy endpoint

The primary endpoint of this study is the rate of disability progression, assessed with Area Under the Curve (AUC) of the CombiWISE scores during the 2-year treatment period. The CombiWISE data collected during the 1-year pre-treatment period will be utilized by including both the pre-treatment disability progression (AUC of CombiWISE scores during the pre-treatment period) and severity of the disability (CombiWISE score at pre-randomization baseline) as covariates in the statistical analysis.

Derivation of CombiWISE scores

CombiWISE is a combinatorial weight-adjusted disability score ranging from 0 to 100, where 0 represents no disability and 100 maximum disability. It was developed based on the pre-determined analysis of 58 candidate outcomes collected in 1 year pre-treatment phase in training (IPPOMS1) and validation (IPPOMS2 and RIVITALISE) cohorts, as described in detail in a recent publication (Kosa, Ghazali et al. 2016). The CombiWISE score is a composite of four scales: expanded disability status scale (EDSS), Scripps neurological rating scale (SNRS), 25 foot walk (25FW) and 9 hole peg test (9HPT) performed on non-dominant hand (NDH- 9HPT). The score is calculated with the following formula:

$$\begin{aligned} \text{CombiWISE} = & 33.166 + 3.803 \times \text{EDSS} - 0.407 \times \text{SNRS} + \\ & 2.409 \times \log(25\text{FW}) + 18.056 \times 25\text{FW}_{\text{fail}} + \\ & 1.305 \times \log(\text{NDH-9HPT}) + 10.751 \times \text{NDH}_{\text{fail}}. \end{aligned}$$

The components of the CombiWISE are derived as follows:

- EDSS: the EDSS score (scored as 1.0, 1.5, ..., 10.0) is recorded as such and requires no derivation.
- SNRS: the SNRS score, which can range between 100 (normal status) and 0 (worst possible score) is recorded as calculated by the investigator.
- $\log(25\text{FW})$ is \log_2 of the average of two attempts on 25FW, or 0 if at least one attempt is unsuccessful.
- $25\text{FW}_{\text{fail}}$ is 1 if patient failed either of the two attempts on 25FW; otherwise 0.
- $\log(\text{NDH-9HPT})$ is \log_2 of average of two attempts on 9HPT with non-dominant hand, or 0 if at least one attempt is unsuccessful.

- NDH_{fail} is 1 if patient failed either of the two attempts on 9HPT with non-dominant hand; otherwise 0.

Calculation of AUC values

The CombiWISE is assessed at the following time points:

- Pre-treatment baseline phase: Months -12, -6 and 0
- Double-blind phase: Months 6, 12, 18 and 24.

The AUC values will be calculated for both the pre-treatment baseline phase (from Months -12, -6 and 0) and for the double-blind phase (from Months 0, 6, 12, 18 and 24). For each of the AUC values, at least two valid CombiWISE scores during the phase in question are required. If less than two values AUC values are available for any of the two phases, the AUC score will be set as missing. In addition, if the first value of the phase in question is missing, the CombiWISE score will be set as missing.

Linear trapezoidal method will be used to calculate the AUC values. For each time interval (time between two visits), the AUC is calculated as $0.5 \times (Y_1 + Y_2) \times (t_2 - t_1)$, where Y_1 and Y_2 are the CombiWISE scores (as changes from baseline) at the beginning and end of the interval and t_1 and t_2 are the start and stop dates of the interval. The time will be converted to years (number of days divided by 365.25) for the AUC calculation. The baseline for the pre-treatment period is the visit scheduled at the beginning of the pre-treatment period (Month -12) and the baseline for the double-blind period is the visit at Month 0.

In case of intermittent missing data between two non-missing visits, the formula for linear trapezoidal method will be used as such. In case of premature discontinuations, the AUC values after the time of discontinuation will be set as missing.

After these calculations, the AUC values calculated for the different periods will be summed over the pre-treatment baseline phase (Month -12 to Month 0) and over the double-blind phase (Month 0 to Month 24). Because the follow-up times can vary from patient to patient, the AUC values will be made comparable by scaling them using the follow-up time. The scaling will be done by dividing the AUC value by the square of the actual duration of each of the phases. For the pre-treatment baseline phase, the AUC will be scaled as $AUC/[t_0 - t_{-12}]^2$, where t_0 and t_{-12} are the dates of visits at Month 0 and Month -12, respectively. For the double-blind phase, the AUC will be scaled as $AUC/[t_{last} - t_0]^2$, where t_{last} and t_0 are the dates of the last visit and the visit at Month 0, respectively. Similarly as above, the time will be converted to years. The scaled AUCs will be used in all statistical analyses.

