7.2 Recruitment

This protocol will be advertised on the NIH website and through patient support groups such as the National MS Society (NMSS). Active recruitment will include a letter to neurologists in the greater Washington DC area and to MS specialists in the states of Virginia, West Virginia, Maryland, Delaware, New Jersey and Pennsylvania. We have contracted the recruitment services of the North American Research Committee on Multiple Sclerosis (NARCOMS). The NARCOMS registry is a database of MS patient volunteers who are interested in participating in research. NARCOMS collects volunteer data, and then will match the volunteers to applicable studies. Volunteers are then mailed information about the studies they match, and the participant is able to contact the studies they are interested in. Finally, eligible patients will also be recruited from NIB natural history protocols (09-N-0032 and 89-N-0045). Because this natural history protocol collects identical clinical, MRI and paraclinical data as the present protocol, we will use data already collected under the natural history protocol in order to fulfill the requirements of the pre-treatment baseline. This will allow eligible PP-MS patients to proceed to the randomization and treatment phase of the current protocol without unnecessary delay.

Patient advertisement (for NIH website and for NMSS bulletin) and the letter to the neurologists are provided in Appendix F.

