11.3 Handling of missing/unobtainable data

All efforts will be made to collect a complete set of data by employing 1-2 week flexibility in scheduling and repeating inadequate quality MRI scans.

With the exception of the primary endpoint (AUCs) and the sensitivity analyses, for continuous and categorical endpoints, no data imputation will be made and missing data will be handled by the models itself.

The following single imputation method is applicable for handling of missing data to calculate AUCs of CombiWISE scores and MRI data.

If particular data points are missing for reasons other than inability to perform the test (i.e. because of disability) we will replace the missing data according to following algorithm:

- a. For data obtained every 6 months (i.e. clinical data and brain MRI data), the missing time point will be substituted by the average of 2 adjacent time-points: i.e. 6 months before and 6 months after the missing time-point. If the last time-point is missing (i.e. month 24), we will substitute the data for this time-point by the average of 2 preceding time-points.
- b. For data obtained once at baseline and once at treatment phase (i.e. CSF), the missing data cannot be replaced and the patient will be eliminated from analysis.

Handling data missing because the patient was unable to perform the test due to disability: this may happen for clinical tests such as timed 25 foot walk (25FW), 9 hole peg test (9HPT) and PASAT. These data will be calculated using the following recommendations from scoring instructions for the MSFC:

- a. 25FW: the inability to perform 25FW will be substituted by the largest Z-score in the MSFC Task force database (i.e. with the slowest time of any patient in the combined dataset used by the Task Force in its published meta-analysis). The largest Z-score in the Task Force dataset is 13.7, therefore, for a subject who could not complete the 25FW $Z_{leg, average} = -13.7$ will be used.
- b. 9HPT: the inability to perform 9HPT will be coded as 777 and the following Z-score calculation formula will be applied:

$$Z_{arm, trial\#} = [(1/777 - \text{Baseline mean (1/9HPT)}) / \text{Baseline SD (1/9HPT)}]$$
- c. PASAT: In the event an individual patient cannot complete PASAT-3 due to disability, a score of 0 will be assigned.

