13.1 Primary endpoint: AUCs of CombiWISE scores

13.1.1 Primary analysis

The AUCs of the CombiWISE scores will be analyzed using an Analysis of Covariance (ANCOVA) model with the AUC of the pre-treatment CombiWISE scores, Baseline (Month 0) CombiWISE score and Baseline (Month 0) age as covariates.

The incomplete data in the CombiWISE scores during the 2-year treatment period will be managed with the single imputation algorithm defined in Section 4.2.

In addition to the primary analysis comparing the between-group difference, the within group changes will be tested using paired t-test within each treatment group. The t-tests will be based on Satterthwaite's approximation.

The analyses will be conducted both using the ITT population (primary) and Completer population (secondary).

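### A missing Month -12 CombiWISE score would drop a randomised patient from the primary ANCOVA, because the pre-treatment AUC covariate has no fill-in rule

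*SAP*

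**What the plan says.** SAP 4.2 builds the pre-treatment AUC from Months -12, -6 and 0. "The baseline for the pre-treatment period is the visit scheduled at the beginning of the pre-treatment period (Month -12"), so scores enter as changes from Month -12, and the area is divided by the squared time from Month -12 to Month 0. Two valid scores in a phase are required. A further condition follows: "if the first value of the phase in question is missing, the CombiWISE score will be set as missing".

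SAP 13.1.1 fits the primary ANCOVA "with the AUC of the pre-treatment CombiWISE scores, Baseline (Month 0) CombiWISE score and Baseline (Month 0) age as covariates", in the ITT population. On gaps it says only this: "The incomplete data in the CombiWISE scores during the 2-year treatment period will be managed with the single imputation algorithm", and refers back to 4.2.

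Protocol 11.3 has its own single imputation: "the missing time point will be substituted by the average of 2 adjacent time-points: i.e. 6 months before and 6 months after". It adds a rule for a missing final visit (Month 24) and none for a missing first visit. The SAP's opening statement gives the SAP precedence where the two differ.

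The ITT definition in SAP section 8 asks for randomisation and one efficacy assessment after Month 0. Protocol 11.2 places the primary analysis in everyone randomised. Neither makes a pre-treatment AUC a condition of entry.

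**The concern.** The pre-treatment AUC only adjusts the comparison; the outcome is the treatment-period AUC. A rule that is reasonable for an outcome does a different job when applied to a covariate, because it can remove a patient whose outcome is fully observed. Someone with scores at Months -6 and 0 and at every treatment visit meets the two-score condition, then loses the covariate through the first-value rule. The primary analysis would then cover fewer patients than the population it names. The plan does not say how such a patient is handled, so the choice could be made after the data are seen. At stake are some precision in a trial of 66 and the match between the stated and the actual analysis set.

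**Working it through.** **1. Following the rule through.** Take a randomised patient with every score except Month -12.
- SAP 4.2: two valid scores exist, but the first-value rule applies. Read literally, the sentence blanks the CombiWISE score rather than the AUC. The result is the same, because change from Month -12 cannot be formed without a Month -12 score.
- SAP 13.1.1: the covariate is missing, and the stated fill-in covers treatment-period scores only.
- Protocol 11.3: averaging needs a visit on each side, and Month -12 has none before it.
- An ordinary least-squares ANCOVA uses only patients with every model variable present. A trial fit on dummy data with 66 complete outcomes and 3 missing covariate values used 63 patients.

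**2. The SAP's own power table (SAP 6.2).** Inputs: untreated mean AUC 51.24, SD 46.2, correlation 0.5, two-sided alpha 0.05. The SD of a paired difference is 46.2 × √(2 × (1 − 0.5)) = 46.2. An exact paired t calculation gives minimum pairs of 28, 34, 42, 55, 73, 105 and 162 for effects of 50% down to 20%. All seven match the table. Power is 0.8075 at 28 pairs and 0.8016 at 42 pairs, against 80.7 and 80.2 in the table.

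**3. Cost of losing patients between arms.** The same inputs are carried to a two-arm ANCOVA. The assumption is that the pre-treatment SD and the 0.5 correlation hold between covariate and outcome in the treatment period.
- Residual SD = 46.2 × √(1 − 0.5²) = 40.0.
- Noncentrality = difference ÷ (40.0 × √(1/n₁ + 1/n₂)), with n₁ + n₂ − 2 − 3 degrees of freedom (three covariates).
- 50% effect: difference 0.5 × 51.24 = 25.62. At 33 per arm, noncentrality is 25.62 ÷ (40.0 × √(2/33)) = 2.60 on 61 df.

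The number lost, k, is not in the documents, so a range is shown.

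| k lost of 66 | Power, 50% effect | Power, 40% effect |
|---|---|---|
| 0 | 0.726 | 0.535 |
| 1 | 0.719 | 0.529 |
| 3 | 0.705 | 0.516 |
| 5 | 0.690 | 0.502 |
| 10 | 0.652 | 0.468 |

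The loss is about 0.6 to 0.7 percentage points per patient. The k = 0 row is below 80% because the SAP table counts pairs in a paired design; that is a separate matter from this point.

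**4. Two candidate repairs.** Assume visits exactly six months apart and independent visit errors with variance σ².
- Three-visit scaled AUC: −0.75 × Month -12 + 0.5 × Month -6 + 0.25 × Month 0. Error variance is (0.5625 + 0.25 + 0.0625)σ² = 0.875σ².
- Month -6 to 0 only: 0.25 × (Month 0 − Month -6) ÷ 0.5² = Month 0 − Month -6. Error variance is 2.0σ², which is 2.0/0.875 = 2.3 times as large. The weight on Month 0, also the baseline of the outcome, rises from 0.25 to 1.0.
- Mean imputation ignoring arm: the patient stays in with no individual adjustment for this covariate, so the residual SD for that patient is 46.2 instead of 40.0. Relative information is about 40.0²/46.2² = 0.75, against zero if the patient is dropped.

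**The case against.** The strongest reply is that the case should hardly arise. Protocol 7.4 randomises patients who have completed the baseline period. Month -12 is the entry visit with clinical evaluation (Protocol 25.1), and EDSS is an eligibility criterion. Protocol 11.5 describes the one-year baseline analysis in 35 + 34 = 69 patients of this trial and mentions losses of MRI outcomes only. This stands, and it is why the size is put as small.

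Four stronger readings are tempting, and the documents do not support them.
- **Borrowed baseline data make gaps likely.** Protocol 7.2 does say "we will use data already collected under the natural history protocol in order to fulfill the requirements of the pre-treatment baseline", but the same sentence gives as its reason that the natural-history protocol collects identical data.
- **A four-part composite is often missing.** SAP 4.2 scores failed walk or peg-test attempts inside the formula. Only a component that was not recorded leaves a gap.
- **Power falls from 80% to the mid or low 70s.** A reader might start from 80% at 33 per arm and get 77%, 76% and 73% at 31, 30 and 28 per arm. That 80% is the published brain-atrophy figure for a 50% effect, not CombiWISE, and those losses of 4 to 10 patients have no source in the documents.
- **The comparison is biased.** Whether Month -12 exists is settled before allocation, so it cannot depend on arm.

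It is also fair to say that exclusion is inferred from how ANCOVA works and is not stated in the SAP. In addition, the random coefficient model and the MMRM in SAP 13.1.2 can keep these patients: the first uses all observed scores, and the second needs a pre-treatment slope that Months -6 and 0 can supply. Neither estimates the primary AUC contrast, so they do not close the gap.

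**Conclusion.** The point holds as a limited one. Following SAP 4.2 and 13.1.1 as written, with an ordinary ANCOVA, loses an ITT patient whose treatment-period outcome is complete, contrary to the stated analysis population. The cost is precision: about 0.6 to 0.7 percentage points of power per patient dropped, for effects of 40% to 50%. This rests on the SAP's SD and correlation carrying over to the between-arm comparison. The number of patients affected is unknown, may be zero, and is probably small. The change is still worth making because it is nearly free and removes an undefined case from the primary analysis.

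**What to change.** In SAP 4.2 and 13.1.1:
- Limit the first-value rule to the treatment-period outcome and the within-group paired test, and correct CombiWISE score to AUC in that sentence.
- For the ANCOVA covariate only, replace a missing pre-treatment AUC with the mean over all other randomised patients, calculated without regard to arm.
- State that every ITT patient with a treatment-period AUC enters the primary ANCOVA.

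Do not use a Month -6 to 0 AUC as the substitute: its expected value is the same under linear progression, but it is a noisier covariate and leans on Month 0.

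The cost is a few sentences. Filling in a baseline covariate without using the arm does not bias a randomised comparison. The small downside is that the patients concerned get no individual adjustment for pre-treatment progression. Protocol 7.6 records that the data analysis has been completed, so the rule can also be run as a check, with the number of patients it affects reported.
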